#### **3.6. Adjustment for Multiplicity**

There are no plans to adjust for multiplicity.

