## 2. STUDY SYNOPSIS

This will be a randomized, multi-centered clinical trial. Participants will include preterm neonates diagnosed with neonatal sepsis who are treated with antibiotics. All eligible patients with parental consent, who cannot tolerate enteral feed will be assigned as Group 1 (antibiotic only). All eligible patients with parental consent, who can tolerate enteral feed enrolled into the trial will be randomized into two treatment groups. Group 2 will receive vitamin D as adjuvant therapy (400 IU) for seven days. Group 3 will receive vitamin D as adjuvant therapy (800 IU) for seven days. Each patient will undergo clinical assessments and blood examination at the beginning and end of each treatment period.

Study assessments will include the sepsis score (Tollner score and sepsis prediction score) and C-reactive protein examination.

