### 2.1. Primary Objective

1. To determine the effect on the modified Tollner sepsis score among groups of preterm neonates with sepsis receiving adjuvant Vitamin D therapy at doses of 400 IU/day and 800 IU/day, compared to those receiving antibiotics alone.
2. To determine the effect on the Sepsis Prediction Score among groups of preterm neonates with sepsis receiving adjuvant Vitamin D therapy at doses of 400 IU/day and 800 IU/day, compared to those receiving antibiotics alone.

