## 2.4. Design and Intervention

This study is an analytical experimental study with a randomized controlled trial (RCT) design. All samples that meet the inclusion and exclusion criteria will be enrolled as study subjects. Subject characteristics data will be obtained from the patient's medical records. This was an open-label trial due to the nature of the nutritional intervention (NPO vs. enteral).

Subjects were subsequently allocated into three groups:

- Group 1: Subjects requiring medical fasting (NPO) due to their clinical condition, who received antibiotics alone.
- Group 2: Subjects able to tolerate enteral nutrition, who received antibiotics plus Vitamin D3 supplementation of 400 IU once daily for 7 days.
- Group 3: Subjects able to tolerate enteral nutrition, who received antibiotics plus Vitamin D3 supplementation of 800 IU once daily for 7 days.

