## 2.6. Sample Size

Samples will be drawn from study subjects who meet the inclusion criteria. The determination of the sample size is tailored to the study objectives and the type of data involved. This study utilizes a specific design, namely unpaired (non-paired) categorical-numeric analytical design. Therefore, the determination of the sample size is based on statistical calculation, setting a 95% confidence level and an 80% power of test (power). Thus, the minimum sample size for each group is 19 subjects. Therefore, the total minimum sample size for the three groups is 57 patients.

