#### **3.4. Definition of analysis populations**

Data from this study will be analysed as a per-protocol analysis. Data from all participants who are randomised will be included in the per-protocol analysis.

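### Two unranked primary scores, each with two dose-versus-antibiotics contrasts, have no multiplicity adjustment and no stated rule for what counts as success

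*Combined protocol and SAP*

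**What the plan says.** Section 2.1 lists two items under the primary objective: "To determine the effect on the modified Tollner sepsis score among groups of preterm neonates with sepsis" and "To determine the effect on the Sepsis Prediction Score among groups of preterm neonates with sepsis". Each compares vitamin D at 400 IU/day and at 800 IU/day with antibiotics alone. That makes four named primary contrasts, with no order among scores or doses.

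Section 3.6 reads in full: "There are no plans to adjust for multiplicity". Section 3.1 says the plan covers all objectives, but no section names a test for the scores, an overall gate or a definition of success.

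Section 2.6 describes an "unpaired (non-paired) categorical-numeric analytical design" and continues: "setting a 95% confidence level and an 80% power of test (power). Thus, the minimum sample size for each group is 19 subjects". It does not say which score, contrast or difference the 80% refers to.

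Section 2.4 defines Group 1 as "Subjects requiring medical fasting (NPO) due to their clinical condition, who received antibiotics alone". Only Groups 2 and 3 are formed by randomisation (section 2).

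**The concern.** Leaving several comparisons unadjusted can be defended when one outcome decides the trial, or when all must succeed. This plan states neither. As written, a single p-value below 0.05 among four could be presented as a positive primary result, and which score decides could be settled after the data are seen. If the two scores disagree, the plan offers no way to read the result. Nor can a reader tell what the stated 80% power is power for.

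**Working it through.** **Inputs.** Two scores and two contrasts per score (2.1); no adjustment (3.6); 5% per test, read from the 95% confidence level, and 19 per group (2.6). Assumptions: two-sided tests, comparable groups with no true difference, and any one significant result counts as success. The between-score correlation is not given, so it is varied from 0 to 1.

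**1. The plan's own figure.** The 19 per group cannot be reproduced, because section 2.6 gives no difference or SD. Solved backwards for one two-group comparison at 80% power, d = (1.96 + 0.84) × √(2/19) = 0.91 SD, or 0.93 SD with the exact t-test. The error rates below do not depend on this value.

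**2. One score, two contrasts.** Both doses share the antibiotics-only comparator, so with equal groups their test statistics correlate at (1/19) / (1/19 + 1/19) = 0.5. The chance that at least one exceeds 1.96 in absolute value is 9.1% (bivariate normal).

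**3. Two scores, four contrasts.** If the scores are perfectly correlated, the second adds nothing and the rate stays at 9.1%. If they are uncorrelated, it is 1 − (1 − 0.0907)² = 17.3%. Four fully independent tests would give 1 − 0.95⁴ = 18.5%, but that does not apply because the comparator is shared.

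**4. Other tests the plan might mean.** Simulated trials with 19 per group and normal scores give the chance of at least one false positive:

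| Analysis | corr. 0 | 0.5 | 0.8 | 1 |
|---|---|---|---|---|
| Four pairwise t-tests | 17.3% | 16.1% | 14.0% | 9.0% |
| One three-group ANOVA per score | 9.8% | 9.2% | 7.9% | 4.9% |
| Pairwise tests only after a significant ANOVA | 8.2% | 7.7% | 6.7% | 4.1% |
| Randomised 400 v 800 IU, both scores | 9.7% | 9.2% | 7.9% | 5.1% |

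The uncorrelated ANOVA figure agrees with 1 − 0.95² = 9.75%. Unequal groups move the four-test range little: 9.5-18.0% if Group 1 is twice the size of each dose group, and 8.5-16.3% if each dose group is twice the size of Group 1.

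**5. Do candidate rules hold 5%?** Three were simulated.
- Rule A: one deciding score, Holm across its two contrasts, and the other score tested the same way only if both are significant.
- Rule B: for each dose take the larger of the two scores' p-values, then Holm across doses.
- Rule C: 0.025 per score, Holm within each score.

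Across the global null and three configurations with some true effects, at correlations 0 to 0.9, the highest family-wise error was 5.0% for A, 5.0% for B and 4.9% for C.

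**6. Power cost at 19 per group.** Assume both doses differ from Group 1 by 0.93 SD on both scores, so that one unadjusted t-test has 80% power. Rule A finds at least one dose on the deciding score in 85% of trials and both in 67%. As the doses have equal effects, power for a named dose is (85 + 67)/2 = 76%. Rule B finds at least one dose in 68-85% (correlation 0 to 1). Rule C has about 65% power for a named dose on a given score.

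**The case against.** The strongest reply is that the plan is open: both scores are named as primary, non-adjustment is declared, and dropping an unfavourable score would be visible. Some statisticians accept that for a small trial with full reporting. It answers concealment, but it does not supply a rule for reading two primary scores that may disagree.

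A second reply is that four ungated pairwise tests may not be intended. Section 2.1 speaks of effects among groups, and the baseline table in section 4.2 has one p-value column across three groups, which fits an overall test at least as well. This stands. It is why 9-17% cannot be given alone and why the lower ranges sit beside it. Under an overall test per score, or pairwise tests gated by one, the rate falls to 5% or below only when the scores are almost perfectly correlated.

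A third reply is that the fasting comparator is the larger problem. That also stands. Illness severity could produce a significant Group 1 contrast at any adjusted alpha. It is a separate flaw and does not remove this one.

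A reader might also infer from section 3.4, which says "Data from all participants who are randomised will be included in the per-protocol analysis", that Group 1 is left out of the analysis. The documents as a whole do not support that: sections 2.3.1 and 2.6 count 19 per group in three groups, and section 4.2 has a control column. The wording of 3.4 needs its own correction.

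**Conclusion.** The concern holds as a missing decision rule. From multiplicity alone, the chance of at least one false-positive primary result is about 9-17%, 5-10% or 4-8%, depending on which test for the named contrasts is meant, and 5-10% for 400 v 800 IU on both scores. This rests on any one result counting as success, two-sided 5% tests, about 19 per group and a between-score correlation anywhere from 1 to 0.

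Two stronger readings are not supported. A reader might take 9-17% as this trial's false-positive rate. It is not: the calculation assumes comparable groups, whereas Group 1 is defined by inability to feed, and the plan names no test. A reader might also infer that the trial must be enlarged. The documents give no effect size from which to derive such a need, and the rules can be adopted at 19 per group if the lower power is stated.

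**What to change.** Before outcome data are examined, replace section 3.6 with one rule that names the test, lists the primary contrasts and says how the two scores are combined. For example, rule A: name one deciding score, test its two contrasts with Holm at two-sided 5%, and test the other score the same way only if both are significant, otherwise reporting it as exploratory. Rules B and C are acceptable alternatives; the choice is the sponsor's.

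Whichever rule is chosen, label every Group 1 contrast as non-randomised, and state in section 2.6 which outcome, contrast and difference the 80% power covers, with the power under the rule.

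The cost is SAP wording and some power: under the assumptions above, 80% falls to about 76% for a named dose on the deciding score under rule A, or to about 65% for a named dose on a given score under rule C. No extra patients are needed if the lower figure is stated.

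Timing is unclear, because sections 2.4, 2.5.1 and 3.7 are partly in the past tense. If outcome data have already been examined, label the rule post hoc and report all four results.

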#### **3.7. Interim Analyses**

[figure not shown]
Interim analysis was not performed.

#### **3.8. Handling of Missing Data**

It is inevitable that some data will be missing. If less than ten percent of the total data is missing then no change to the analysis will be made.

## 4 DESCRIPTIVE STATISTICS

### 4.1. Recruitment and Follow-up

#### 4.2. Baseline Characteristics

Baseline population will be summarised using mean and standard deviations or median and interquartile range.

Variable	Control (n=...)	Vitamin D 400 IU (n=...)	Vitamin D 800 IU (n=...)	p value
Gender, n (%)				
Male				
Female				
Age (days), Mean/Median (SD/IQR)				
Gestational age (weeks), Mean/Median (SD/IQR)				
Gestational age, n (%)				
32–<37 weeks				
28–<32 weeks				
Birth weight (gram), Mean/Median (SD/IQR)				
Birth weight, n (%)				
<1000 gram				
1000–<1500 gram				
1500–<2500 gram				
≥2500 gram				
Respiratory support, n (%)				
Low Flow				
CPAP/NIV				
Ventilator				
Vitamin D (ng/mL), Mean/Median (SD/IQR)				
Classification of vitamin D status				
Sufficient				
Insufficient				
Deficient				

